2. INTRODUCTION

Vulvovaginal atrophy is an inflammation of the vagina (and the outer urinary tract) due to the thinning and shrinking of the tissues, as well as decreased lubrication. These symptoms are due to a lack of the reproductive hormone estrogen.

The most common cause of vaginal atrophy is the decrease in estrogen which happens naturally during perimenopause, and increasingly so in post-menopause. Vaginal atrophy symptoms usually appear 4-5 years after the onset of menopause and can affect up to 50% of women. The symptoms can include vaginal soreness and itching, as well as painful intercourse, and bleeding after sexual intercourse. The shrinkage of the tissues and loss of flexibility can be extreme enough to make intercourse impossible.

The primary goal of vaginal atrophy treatment is to restore the normal physiological conditions of the vagina, this reducing the symptoms.

Various therapies have been used to treat this condition – herbs, lubricants, and hormonal treatments. However, the results of these treatments are transitory and limited to the vaginal mucosa.

Lasers, particularly fractional CO₂ lasers, have shown much promise as a treatment with a lasting effect. The fractional CO₂ laser can induce permanent molecular changes, stimulating the growth of new collagen and the activation of fibroblasts.

There have been other clinical studies successfully using fractional CO₂ lasers for the treatment of vaginal atrophy.

In a 2013 study, 48 post-menopausal women were treated with a vaginal fractional CO₂ laser from Deka. The data indicated significant improvement in VVA symptoms in women who had undergone 3 fractional CO₂ laser sessions. Overall, 91.7% were satisfied or very satisfied with the procedure and experienced considerable improvement in their quality of life. This study was published in *Maturitas*, the European menopause journal - *Vulvo-vaginal atrophy: A new treatment modality using thermo-ablative fractional CO₂ laser* (Antonino Perino, Alberto Calligaro, Francesco Forlani, Corrado Tiberio, Gaspare Cucinella, Alessandro Svelato, Salvatore Saitta, Gloria Calagna).

In 2014, another study was published in the *Journal of Endometriosis and Pelvic Pain Disorders* 2014: 6(3) 150-156 entitled *Microablative fractional CO₂ laser improves dyspareunia related to vulvovaginal atrophy: a pilot study* (Stefano Salvatore, Umberto Leone Roberti Maggiore, Massimo Origoni, Marta Parma, Lavinia Quaranta, Filomena Sileo, Alice Cola, Ilaria Bainsi, Simone Ferrero, Massimo Candiani, Nicola Zerbinati). In this study, the laser treatment was efficacious in improving dyspareunia in 100% of the 15 patients included in the study. The intensity of dyspareunia significantly decreased from baseline (8.7 ± 1.0) to 12 week follow-up (2.2 ± 1.0 ; $p < 0.001$). In addition, all other VVA symptoms significantly ameliorated at the same follow-up.

Another 2014 study, published in the journal **Climacteric**. 2014 Aug;17(4):363-9 and entitled *A 12-week treatment with fractional CO₂ laser for vulvovaginal atrophy: a pilot study* (Salvatore S, Nappi RE, Zerbinati N, Calligaro A, Ferrero S, Origoni M, Candiani M, Leone Roberti Maggiore U), showed that fractional CO₂ laser treatment for VVA was effective ($p < 0.001$) to improve VVA symptoms in 50 post-menopausal women dissatisfied with previous local estrogen therapies.

3. STUDY OBJECTIVE

This single-center study objective is to assess the safety and efficacy of the Edge One CO₂ laser and laser handpiece in the treatment of vulvovaginal atrophy (VVA), particularly for vaginal dryness.

4. STUDY DEVICE

The CO₂ laser will be provided by Perigee Medical and will be stored in a locked room at the study center site. An accurate record of the module usage and settings should be maintained by the Principal Investigator. Using pre-determined settings, each patient will be treated 3 times over an 12 week period.

Figure 1: CO2 handpiece

Please note that the Edge CO2 laser with the fractional handpiece has an FDA clearance (K100590). The fractional handpiece has a general clearance for ablative skin resurfacing. The handpiece to be used is a variation of the FDA cleared handpiece, and it does not have an FDA clearance. It does bear a CE mark internationally for this indication for use. The purpose of this study is to determine the efficacy and feasibility of the Perigee Medical Edge CO2 laser with fractional handpiece for the treatment of a specific gynecology issue – vulvovaginal atrophy.

5. INVESTIGATIONAL PLAN

5.1 Study Design

The study design will be a prospective study with a total of up to 30 post menopausal subjects clinically diagnosed with vulvovaginal atrophy. The subjects will be treated with the fractional handpiece. Subjects will undergo 3 treatments. (Each treatment duration will be approximately 10-15 minutes.)

Before the initiation of the treatment, each subject will undergo a clinical evaluation as noted before. Each subject's vulvovaginal atrophy will be assessed by the clinical physician.

Clinical improvement will be assessed by the patient using a visual analogic scale (VHIS) to determine vaginal dryness. Additionally, patients shall complete a standardized female sexual function index questionnaire (FSFI) at each follow-up visit. Treatment and all results will be documented in a Case Report form.

If adverse side effects are observed, the investigator should provide the subject with the proper care and remedy and will document it in the Case Report Form.

5.2 Study Population

Subjects for this study will be recruited from the existing patient base at the study site. IRB approved e-mails and fliers may also be used for the recruitment of subjects. Up to 25 healthy

evaluable subjects will participate in this study. An evaluable subject is one who has passed the inclusion and exclusion criteria; given informed consent; received and followed the treatment schedule, and has been adequately followed to establish valid endpoints of efficacy.

5.2.1 Inclusion Criteria

Subjects meeting the following inclusion criteria may participate:

- Healthy non-smoking post menopausal women with absence of menstruation of at least 6 months
- Exhibiting VVA symptoms
- Prolapse staged \leq II, according to the pelvic organ prolapse quantification (ICS-POP-Q) system
- Have not had procedures in the anatomical area through 6 months prior to treatment
- Understand and accept the obligation and is logistically able to present for all scheduled follow-up visits

5.2.1 Exclusion Criteria:

Subjects meeting any of the following criteria will be excluded from participation:

- Acute or recurrent urinary tract infection (UTI), or genital infection (e.g. herpes candida).
- Prolapse staged $>$ II, according to the pelvic organ prolapse quantification (ICS-POP-Q) system
- Any serious disease, or chronic condition, that could interfere with the study compliance
- Previously undergone reconstructive pelvic surgery
- Have used vaginal creams, moisturizers, lubricants or homeopathic preparations for at least 3 months
- Have taken antiviral treatments
- Have a mesh (slings are acceptable)
- A history of thrombophlebitis
- A history of acute infections
- A history of heart failure
- Received or is anticipated to receive antiplatelets, anticoagulants, thrombolytics, vitamin E or anti inflammatories within 2 weeks pre treatment
- Any medical condition, that, in the investigator's opinion would interfere with the patient's participation in the study
- Taking medications that are photosensitive
- A history of keloid formation

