5.2.3 Concomitant/Excluded Skin therapies and Medications

Subjects are not allowed to take take Premarin, Estrace 17 Beta Estradiol vaginal cream, Vagifem, or Estring (within 30 days) of the treatments. Subjects cannot have used topical prescription or over the counter meds in the treatment area within 30 days of a treatment. Subjects will be instructed not to take any prescription medications (except those allowed by protocol), without prior consultation with the Investigator. If concomitant therapy must be added then the reason, the name of the drug/product, the daily dose, and date of initiation and/or discontinuation of therapy will be recorded on the Concomitant Medication Page of the Case Report Form.

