6.2 Treatment Regimen

A total of up to 30 subjects will be assigned to receive CO2 fractional treatments for vulvovaginal atrophy. Treatments will be repeated every 4 weeks for a total of up to 3 treatments.

Concomitant use of other prescription or OTC medications in the treatment area is not permitted while in the study.

If the subject is unable to tolerate the treatments, then the subject will be discontinued. If the patient is discontinued, they will come in for a 1 month follow up visit after the treatment to ensure patient safety.

If strong reactions occur after any treatment, these subjects should be treated according to the best judgment of the Principal Investigator. This information is to be appropriately documented on the CRFs.

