6.4.2 Screening Visit/Baseline

Prior to study initiation, each subject will be screened to ensure they meet all of the inclusion and none of the exclusion criteria outlined above. Potential subjects will be interviewed and examined by Investigator or his designee to establish their eligibility for inclusion in the study. Subjects will be given a full description of the nature and purpose of the study. If a subject is willing to participate, they must provide written informed consent before proceeding with the study. This visit will take approximately 1 hour.

Screening procedures will include the following activities for prospective participants:

1. Investigator, or designee, explains the investigational study and eligibility requirements.
2. Subject signs informed consent prior to any study-related procedures.
3. Investigator determines eligibility criteria.
4. Brief medical history.
5. Investigator assessment of vaginal dryness using a visual analogic scale (10cm VAS)

6.4.3 Treatment will take approximately 10-15 minutes.

1. Query for concomitant products/medications.
2. Exam of the treatment area.
3. Subject will receive treatment for vulvovaginal atrophy
5. Adverse event evaluation.

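### The 5.2.1 exclusion for vaginal creams, moisturizers and lubricants sets a length of use with no look-back, so current use of non-medicated products at the baseline dryness rating is not clearly ruled out

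*Protocol*

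**What the plan says.** The exclusion list in Protocol 5.2.1 opens with "Subjects meeting any of the following criteria will be excluded from participation", and one item on it is "Have used vaginal creams, moisturizers, lubricants or homeopathic preparations for at least 3 months". Other items in 5.2.1 are dated. The inclusion list has "Have not had procedures in the anatomical area through 6 months prior to treatment", and the exclusion for antiplatelets, anticoagulants and anti-inflammatories counts back two weeks before treatment.

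Section 5.2.3 has its own rule for an overlapping set of products. For named vaginal oestrogens: "Subjects are not allowed to take take Premarin, Estrace 17 Beta Estradiol vaginal cream, Vagifem, or Estring (within 30 days) of the treatments". For other topical products: "Subjects cannot have used topical prescription or over the counter meds in the treatment area within 30 days of a treatment". Section 6.2 adds "Concomitant use of other prescription or OTC medications in the treatment area is not permitted while in the study". Section 6.5.6 tells subjects to avoid vaginal oestrogen before, during and after the procedures. Section 6.8 discontinues subjects who use concomitant medications or therapies. Section 8.2.2 removes users of unapproved medications or therapies from the efficacy analysis.

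The primary endpoint in 8.2.2 is the change from baseline in dryness on a 10 cm VAS. Section 6.4.2 lists "Investigator assessment of vaginal dryness using a visual analogic scale (10cm VAS") among the screening/baseline activities. Sections 6.5.1 and 7.1 also require a VAS before each treatment. The step "Query for concomitant products/medications" stands among the treatment-visit steps in 6.4.3, although the 6.4.1 schematic does record medication at baseline.

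**The concern.** Creams, moisturizers and lubricants are used to relieve dryness, the symptom that the primary endpoint scores. A restriction on them protects a change-from-baseline endpoint only if it fixes a product-free period before the baseline rating. The 5.2.1 item asks how long a woman used a product, not when she stopped.

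Two things are at stake. First, eligibility: past users are turned away for no reason connected with the endpoint, and some current users are let in. Because 8.2.2 restricts the efficacy analysis to women who meet all entry criteria, the reading chosen also decides who is analysed. Second, the baseline: if some women are rated on product and later rated off it, the mean change contains a product-withdrawal component. There is no control arm against which to separate it.

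**Working it through.** **Step 1. Apply the rules to four hypothetical women.** The washout column reads 5.2.1 as no use in the 3 months before baseline or treatment. That reading is an inference; the protocol does not state it.

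| Woman | 5.2.1 as written | 5.2.1 read as a 3-month washout | 5.2.3 (30 days before a treatment) |
|---|---|---|---|
| A. Cream for 4 months, stopped 60 days before first treatment | Excluded (4 months is over 3) | Excluded (60 days is under 3 months) | Acceptable (60 is over 30) |
| B. Lubricant for 3 months, stopped years ago | Excluded | Acceptable | Acceptable |
| C. Medicated cream for 2 months, in use until baseline, then stopped; first treatment more than 30 days later | Not excluded (2 months is under 3) | Excluded, counting from baseline | Acceptable |
| D. Moisturizer or lubricant for 10 weeks, still in use at baseline | Not excluded (10 weeks is under 3 months) | Excluded | Barred only if the product counts as a medication and is used within 30 days of a treatment |

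B and D show the wording defect: a long-past user is excluded and a current user is not. A shows the mismatch of periods for creams, which is a clash of periods only on the washout reading. C and D show how a baseline can be rated on product.

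**Step 2. Check the reference date.** The 30 days in 5.2.3 run back from a treatment. The baseline VAS in 6.4.2 belongs to a screening/baseline visit that the 6.4.1 schematic shows separately from the first treatment. No interval between the two is stated. If baseline falls within 30 days before the first treatment, 5.2.3 covers medicated products at baseline. If it falls earlier, 5.2.3 does not.

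**Step 3. Check the other restrictions.** Sections 6.2, 6.5.6, 6.8 and 8.2.2 concern medications, therapies or vaginal oestrogen. None names moisturizers or lubricants, and none sets a product-free period before the baseline rating. They narrow case C. They leave case D open unless such products count as medications or therapies.

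**Step 4. Direction and scale.** Let d be the amount by which a product lowers the dryness VAS, p the share of women on product at baseline, and q the share on product at follow-up. With improvement defined as baseline minus follow-up:

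shift in mean improvement = (q - p) x d

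The protocol gives none of p, q and d, so these figures are assumptions:

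- q = 0, p = 0.2, d = 2 cm: (0 - 0.2) x 2 = -0.4 cm
- q = 0, p = 0.4, d = 2 cm: (0 - 0.4) x 2 = -0.8 cm
- wider range with q = 0: p = 0.1, d = 1 cm gives -0.1 cm; p = 0.5, d = 3 cm gives -1.5 cm

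The negative sign means that improvement is understated. If q exceeded p, the shift would be positive. The protocol states no figure of its own to reproduce here.

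**The case against.** The strongest reply is that 5.2.1 and 5.2.3 are cumulative: one is an entry criterion, the other a concomitant-use rule tied to each treatment, and a woman must satisfy both. A reader might infer a flat contradiction between 3 months and 30 days, but the text does not support that. Two periods for one product appear only if 5.2.1 is read as a washout. An entry rule and an on-treatment rule may also legitimately differ. This part of the objection stands. What remains is that the protocol does not say which reading it intends.

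A reader might also infer that a woman can be rated at baseline on vaginal oestrogen and comply with the protocol as a whole. That goes too far. It needs a gap of at least 30 days between baseline and first treatment, which the protocol neither states nor rules out, and 6.5.1 would allow a rating close to treatment. Consent comes before the VAS in 6.4.2, so such a woman is arguably already in the study and in breach of 6.2. Sections 6.5.6, 6.8 and 8.2.2 point the same way. The medicated-product part of the concern is therefore weaker, and the main exposure is non-medicated products.

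Finally, 7.1 has the investigator rate from visual appearance, so relief that a woman feels need not carry over fully to this VAS. That is fair: d could be small. It bears on the size of the shift, not on the wording defect.

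**Conclusion.** The point holds in limited form. It is certain from the text that the 5.2.1 item lacks a look-back and a reference date, and that read literally it sorts women wrongly for a change-from-baseline dryness endpoint. Baseline contamination is possible, not established. It concerns mainly non-medicated moisturizers and lubricants, and medicated products only if baseline precedes first treatment by more than 30 days.

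Three further inferences are not supported. The flaw does not by itself favour the device: baseline on product and follow-up off product would tend to understate improvement, although unequal use could bias either way. The 0.4-0.8 cm is not an estimate, because the share of users and the product effect are both assumed. Nor would the ambiguity produce differences between sites, since this is a single-centre study; at most, screening decisions within the centre may vary.

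The wording should be corrected because it affects eligibility, the baseline and membership of the efficacy set.

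**What to change.** 1. Reword the 5.2.1 item as a look-back: no use of the listed products within a stated period, ending on a stated reference date no later than the baseline VAS.
2. State whether moisturizers and lubricants fall under 5.2.3 and under the ban in 6.2.
3. Reconcile the 3-month and 30-day periods, or state that they are separate rules for separate purposes. The choice of period is the sponsor's.
4. Define the primary baseline as the VAS that 6.5.1 and 7.1 already require before the first treatment, taken once the product-free period is complete, and check that the 6.4.1 schematic shows that rating at the first treatment visit.

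The cost is wording in 5.2.1, 5.2.3 and 6.2 and a definition of baseline. No visit or test is added. The downside is that some women will have to wait out the period before baseline.

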5.2.3 Concomitant/Excluded Skin therapies and Medications

Subjects are not allowed to take take Premarin, Estrace 17 Beta Estradiol vaginal cream, Vagifem, or Estring (within 30 days) of the treatments. Subjects cannot have used topical prescription or over the counter meds in the treatment area within 30 days of a treatment. Subjects will be instructed not to take any prescription medications (except those allowed by protocol), without prior consultation with the Investigator. If concomitant therapy must be added then the reason, the name of the drug/product, the daily dose, and date of initiation and/or discontinuation of therapy will be recorded on the Concomitant Medication Page of the Case Report Form.

5.2.4 Informed Consent

At the initial screening, each prospective subject will be given a full explanation of the nature and purpose of the study by qualified staff of the clinical study site. Once the essential information has been provided to the subject and the Investigator is assured that an individual candidate understands the implications of participating in this study, the subject will be asked to give consent to participate in the study by signing an informed consent form. This consent must

be witnessed and dated and retained by the Investigator as part of the study records. Each subject's signed informed consent form will be kept on file by the Investigator. A copy of the informed consent form will be provided by the Investigator to the subject.

5.2.5 Subject Identification and Confidentiality

Subjects will be identified on the study CRFs by their subject number and/or their initials. CRFs are confidential documents and will only be available to the Investigator, Perigee Medical's representative and the IRB.

5.2.6 Subject Compensation

There will be no subject compensation.

6. STUDY CONDUCT

The study will be conducted at a single center associated with [name], the lead investigator.

6.1 Assignment of Subject Numbers

Each subject who satisfies the inclusion and exclusion criteria will be assigned a number for treatment in accordance with their chronological order of qualification for the study. Once a treatment number has been assigned to a subject it cannot be re-assigned to any other subject.

6.2 Treatment Regimen

A total of up to 30 subjects will be assigned to receive CO2 fractional treatments for vulvovaginal atrophy. Treatments will be repeated every 4 weeks for a total of up to 3 treatments.

Concomitant use of other prescription or OTC medications in the treatment area is not permitted while in the study.

If the subject is unable to tolerate the treatments, then the subject will be discontinued. If the patient is discontinued, they will come in for a 1 month follow up visit after the treatment to ensure patient safety.

If strong reactions occur after any treatment, these subjects should be treated according to the best judgment of the Principal Investigator. This information is to be appropriately documented on the CRFs.

6.3 Subject Instruction

The Investigator or Study Coordinator will thoroughly explain all procedures to the subjects.

Subjects are to be instructed as to the following:

1. Specifics of treatment dosing as discussed above.
2. Not to apply medications of any kind to the treatment area.

6.4 Study Visits

6.4.1. Schematic of Study Visits and Procedures

The evaluations scheduled for each visit are listed below and summarized in the Schematic of Study Visits and Procedures.

Schematic of Study Visits:

Month of visit	BL	1 Tx1	1 FU1	2 Tx2	2 FU2	3 Tx3	3 FU3	4 FU
Eligibility	√							
Informed Consent	√							
Medical History	√							
Medication	√							
Pelvic exam, pap smear, vaginal maturation index, and vaginal pH	√							
Classification	√							
Vulvovaginal symptom questionnaire	√	√	√	√	√	√	√	
Treatment		√		√		√		
Adverse side effects		√	√	√	√	√	√	
Clinical improvement evaluation			√	√	√	√	√	√
Case report form	√	√	√	√	√	√	√	√

BL = baseline

Tx = treatment

FU = follow-up visit

6.4.2 Screening Visit/Baseline

Prior to study initiation, each subject will be screened to ensure they meet all of the inclusion and none of the exclusion criteria outlined above. Potential subjects will be interviewed and examined by Investigator or his designee to establish their eligibility for inclusion in the study. Subjects will be given a full description of the nature and purpose of the study. If a subject is willing to participate, they must provide written informed consent before proceeding with the study. This visit will take approximately 1 hour.

Screening procedures will include the following activities for prospective participants:

1. Investigator, or designee, explains the investigational study and eligibility requirements.
2. Subject signs informed consent prior to any study-related procedures.
3. Investigator determines eligibility criteria.
4. Brief medical history.
5. Investigator assessment of vaginal dryness using a visual analogic scale (10cm VAS)

6.4.3 Treatment will take approximately 10-15 minutes.

1. Query for concomitant products/medications.
2. Exam of the treatment area.
3. Subject will receive treatment for vulvovaginal atrophy
5. Adverse event evaluation.

